1.2.3.2.3 Deaths

In cancer subjects treated with single agent cabozantinib, death was reported in 10 out of 2410 subjects (0.4%) including death related to AEs in 3 (0.1%). Sudden death was seen in 2 patients (0.1%). [(see latest version of the Investigator's Brochure)].

1.2.3.3 Clinical Pharmacokinetics

Cabozantinib pharmacokinetics as single agent in clinical studies are summarized in [(see latest version of the Investigator's Brochure)].

Population PK analysis of cabozantinib was performed using data collected from 289 cabozantinib-treated subjects from XL184-301, XL184-001, and XL184-201 with solid tumors including MTC following oral administration of 140 mg daily doses. The predicted effective half-life is approximately 55 hours, V/F is approximately 349 L, and CL/F at steady-state is estimated to be 4.4 L/h. The terminal half-life (for predicting drug washout) is approximately 120 hours. Following oral administration of cabozantinib, Tmax ranged from 2 to 5 hours post-dose. Repeat daily dosing of cabozantinib at 140 mg for 19 days resulted in 4- to 5-fold mean cabozantinib accumulation (based on AUC) compared with a single dose administration; steady state was achieved by Day 15. Cabozantinib is highly protein bound in human plasma (\geq 99.7%) (see latest version of the Investigator Brochure).

The PK evaluation of cabozantinib in the pediatric population is ongoing. A population PK analysis did not identify clinically relevant differences in clearance of cabozantinib between females and males or between Whites (89%) and non-Whites (11% [$<4\%$ were Asian]). Cabozantinib PK was not affected by age (20-86 years).

Within a 48-day collection period after a single dose of 14C-cabozantinib in healthy subjects, approximately 81% of the total administered radioactivity was recovered with 54% in feces and 27% in urine.

Results from a PK study of cabozantinib in subjects with renal impairment indicated that the ratios of geometric least squares (LS) mean for maximum plasma concentration (Cmax) and AUCs

Proprietary Information of MD Anderson

(AUC0-t and AUC0-inf) were 19% and 30% higher, respectively, for subjects with mild renal impairment compared to subjects with normal renal function. For subjects with moderate renal impairment, both Cmax and AUCs appeared to be similar when compared to subjects with normal renal function (differences: < 3% and < 7%, respectively). Results from a PK evaluation of cabozantinib in subjects with hepatic impairment indicated that exposure (AUC0-inf) of cabozantinib was increased by about 81% and 63% in subjects with mild and moderate hepatic impairment, respectively.

A high-fat meal increased Cmax and AUC values by 41% and 57%, respectively relative to fasted conditions in healthy subjects administered a single 140-mg oral cabozantinib dose.

Cabozantinib is a substrate of cytochrome P450 (CYP3A4) *in vitro*. Inhibition of CYP3A4 reduced the formation of the cabozantinib N-oxide metabolite by > 80%.

Cabozantinib is a substrate of CYP3A4 *in vitro*. Inhibition of CYP3A4 *in vitro* reduced the formation of the cabozantinib N-oxide metabolite by > 80%. Inhibition of CYP2C9 had a minimal effect on cabozantinib metabolite formation (ie, a < 20% reduction). Inhibition of CYP1A2, CYP2A6, CYP2B6, CYP2C8, CYP2C19, CYP2D6 and CYP2E1 had no effect on cabozantinib metabolite formation. In healthy volunteers, cabozantinib AUC was increased 38% with co-administration of the strong CYP3A4 inhibitor ketoconazole (XL184-007) and decreased 77% with co-administration of the strong CYP3A4 inducer rifampin (XL184-006).

Cabozantinib is a noncompetitive inhibitor of CYP2C8 ($K_{iapp} = 4.6 \mu M$), a mixed-type inhibitor of both CYP2C9 ($K_{iapp} = 10.4 \mu M$) and CYP2C19 ($K_{iapp} = 28.8 \mu M$), and a weak competitive inhibitor of CYP3A4 (estimated $K_{iapp} = 282 \mu M$) in human liver microsome (HLM) preparations. The IC_{50} value was 10.1 μM for CYP2B6 and IC_{50} values were > 20 μM for CYP1A2, CYP2D6, and CYP3A4 isozymes. Cabozantinib at steady-state plasma concentrations ($\geq 100 \text{ mg/day}$ daily dosing for a minimum of 21 days) showed no effect on single-dose rosiglitazone (a CYP2C8 substrate) plasma exposure (Cmax and AUC) in subjects with solid tumors (XL184-008). Cabozantinib is an inducer of CYP1A1 mRNA in human hepatocyte incubations (ie, 75-100% of CYP1A1 positive control β -naphthoflavone induction), but not of CYP1A2, CYP2B6, CYP2C8, CYP2C9, CYP2C19 or CYP3A4 mRNA or isozyme-associated enzyme activities.

Administration of the PPI esomeprazole resulted in no clinically-relevant effect on cabozantinib plasma PK in healthy volunteers (XL184-018).

Cabozantinib is an inhibitor ($IC_{50} = 7.0 \mu M$), but not a substrate, of P-glycoprotein (P-gp) transport activities in a bi-directional assay system using MDCK-MDR1 cells. Therefore, cabozantinib may have the potential to increase plasma concentrations of co-administered substrates of P-gp.

Cabozantinib was shown to be a substrate of drug transporter MRP2 in an *in vitro* assay. Administration of MRP2 inhibitors to subjects may result in increases in cabozantinib plasma concentrations. Therefore, concomitant use of MRP2 inhibitors (eg, cyclosporine, delavirdine, efavirenz, emtricitabine) should be approached with caution, and subjects taking MRP2 inhibitors should be monitored for AEs.

Of interest, There was a differences in PK parameters from the two PopPK analyses (RCC patients and MTC patients) and appears to be result of higher clearance in MTC subjects, but the reason for this is not known (see latest version of the Investigator Brochure).

1.2.3.4 Clinical Activity

In phase 3 clinical trial in subjects with progressive MTC (214 on cabozantinib vs. 109 placebo), the estimated median PFS was 11.2 months for cabozantinib versus 4.0 months for placebo (HR 0.28; 95% CI, 0.19 to 0.40; $p < .001$). Prolonged PFS with cabozantinib was observed across all subgroups including by age, prior TKI treatment, and RET mutation status (hereditary or sporadic). The final analysis of the secondary endpoint of OS included 218 events (217 were required) and showed a trend for increased

Proprietary Information of MD Anderson

survival in the cabozantinib arm. The estimated median OS for the cabozantinib arm was 26.6 months versus 21.1 months for the placebo arm (HR = 0.85; 95% CI 0.64, 1.12; p = 0.2409).

In phase 3 trial of 119 subjects with advanced castrate resistant prostate carcinoma with bone metastases, the enrollment was stopped before the planned study population size of 246; a total of 119 subjects were enrolled. The primary analysis for the ITT population (n=119) did not demonstrate an improvement in the proportion of subjects with a pain response at Week 6 confirmed at Week 12 the cabozantinib arm compared with the mitoxantrone plus prednisone arm; the proportions of subjects experiencing a confirmed pain response were 15% and 17% for the two arms, respectively.

The secondary endpoints were BSR per IRF and OS. BSR was defined as a $\geq 30\%$ decrease in total bone-scan lesion area compared with baseline without soft-tissue disease progression. The analysis of BSR per IRF at Week 12 without progression in soft tissue per mRECIST 1.1 demonstrated a greater improvement in the cabozantinib arm (31%; 95% CI: 20%, 43%) compared with the mitoxantrone plus prednisone arm (5%; 95% CI: 0%, 11%). In the analysis of OS that included 78 deaths out of the 196 pre-specified deaths, the stratified HR was 0.70 (95% CI: 0.44, 1.10).

In phase 3 study in renal cell carcinoma, 658 patients were randomized to either everolimus or cabozantinib. Median PFS was 7.4 months with cabozantinib and 3.8 months with everolimus with median duration of treatment of 7.6 months with cabozantinib and 4.4 months with everolimus. Dose reductions were needed in 60% of subjects treated with cabozantinib and the median average daily dose was 44 mg of cabozantinib. The rate of treatment discontinuation due to adverse events not related to renal-cell carcinoma was 9% in the cabozantinib group.

1.2.3.5 Translational Medicine

Details can be found in the latest version of the Investigator's Brochure.

The study plan is to use cabozantinib with initiation dose is 60 mg daily by mouth. The dose can be reduced to 40 mg then 20 mg a day based on tolerability and adverse effects. Subjects may continue to receive study treatment until they experience unacceptable drug-related toxicity or disease progression. Considering the possibility mitotane induction of CYP3A4 that can reduce cabozantinib levels, subjects who used mitotane within 6 months of study participation will have PK levels (obtained on day 1 and day 29+- 5 days) analyzed after collection to allow increasing cabozantinib dose to 80 mg a day if AUC for plasma cabozantinib was < 50% of expected AUC. Further dose titration in these subjects to 60 mg, 40 mg and 20 mg will be done based on tolerability and adverse effects. In the remaining study subjects (estimated 12 out of 18 patients), samples will be analyzed a-posteriori after completing study enrollment.

2 STUDY OBJECTIVES AND DESIGN

2.1 Study Objectives

The objectives of this study are as follows:

Primary objective: To estimate progression free survival at 4 months

Secondary objectives:

1. Best overall response rate
2. Overall survival (O.S)
3. Toxicity assessment by the Common Terminology Criteria for Adverse Events (CTCAE) V4.0

Exploratory objectives:

1. Pharmacokinetics of cabozantinib plasma levels to assess correlation with response to therapy
2. Steroid hormone biomarkers as markers of disease response.
3. Study the effect of cabozantinib on immune markers by obtaining optional biopsy and blood samples collection at baseline, during therapy and at time of progression.
4. Pharmacogenomics of drug disposition gene variants that potentially influence cabozantinib PK.

Proprietary Information of MD Anderson

2.2 Study Design

2.2.1 Overview of Study Design

This is an open label Phase II clinical trial using cabozantinib in patients with unresectable/advanced ACC.

2.3 Blinding and randomization

N/A

2.4 Study Sites

This study will be conducted The University of Texas MD Anderson IND Office

2.5 Withdrawals

Subjects may discontinue study treatment or withdraw their consent to participate in the study at any time without prejudice. The investigator may withdraw a subject from study treatment or from the study if, in his or her clinical judgment, it is in the best interest of the subject or if the subject cannot comply with the protocol.

In addition, any of the following conditions require discontinuation of the subject from study treatment:

- An AE or intercurrent illness that in the opinion of the investigator warrants the subject's withdrawal from study treatment;
- The investigator believes it is not in the best interest of the subject to continue on study
- Specific conditions described in the Management of Adverse Events Sections 3.3.2 and 3.3.2.1;
- Necessity for treatment with other anticancer treatment prohibited by protocol;
- Sexually active subjects who refuse to use medically accepted barrier methods of contraception (e.g, male condom, female condom) during the course of the study and for 4 months after discontinuation of study treatment;
- Women who become pregnant or are breastfeeding;
- If the subject does not recover from his or her toxicities to tolerable Grade ≤ 2 within 6 weeks, the subject will have study treatment discontinued unless there is unequivocal evidence that the subject is benefitting. In this situation, a subject may be able to restart therapy with a dose reduction upon resolution of the toxicity and with agreement of the principal investigator / MD Anderson IND Office;
- Request by regulatory agencies for termination of treatment of an individual subject or all subjects under the protocol;
- Significant noncompliance with the protocol schedule in the opinion of the investigator;
- The minimum dose of study treatment will be 20 mg once daily (qd). Subjects who cannot tolerate 20 mg qd will have study treatment discontinued;

Proprietary Information of MD Anderson

- Progressive disease (PD) or the subject no longer experiences clinical benefit as determined by the investigator

2.5.1 Replacements

NA

3 TREATMENTS

3.1 Composition, Formulation, and Storage

At study sites, all study medication will be stored as described in the pharmacy manual and inventoried in accordance with applicable state and federal regulations.

3.1.1 Investigational Treatment

Chemical Name: Chemical Name: *N*-{4-[(6,7-dimethoxyquinolin-4-yl)oxy]phenyl}-*N'*-(4-fluorophenyl)cyclopropane-1,1-dicarboxamide, (2S)-hydroxybutanedioate

3.1.2 Cabozantinib Tablets

Exelixis internal number: XL184

Cabozantinib tablets are supplied as film coated tablets containing cabozantinib malate equivalent to 20 mg and 60 mg of cabozantinib and contain microcrystalline cellulose, lactose anhydrous, hydroxypropyl cellulose, croscarmellose sodium, colloidal silicon dioxide, magnesium stearate and Opadry® yellow. All tablet strengths are prepared from a common blend and are distinguished by shape. The 20 mg tablets are round and the 60 mg tablets are oval. The components of the tablets are listed in Table 3-1.

Table 3-1: Cabozantinib Tablet Components and Composition

Ingredient	Function	% w/w
Cabozantinib malate (25% drug load as cabozantinib)	Active Ingredient	31.7
Microcrystalline Cellulose (Avicel PH-102)	Filler	38.9
Lactose Anhydrous (60M)	Filler	19.4
Hydroxypropyl Cellulose (EXF)	Binder	3.0
Croscarmellose Sodium (Ac-Di-Sol)	Disinegrant	6.0
Colloidal Silicon Dioxide,	Glidant	0.3
Magnesium Stearate	Lubricant	0.75
Opadry Yellow Film Coating which includes:		
- HPMC 2910/Hypromellose 6 cp		
- Titanium dioxide	Film Coating	4.00
- Triacetin		
- Iron Oxide Yellow		

3.2 Dose, Schedule and Route

Subjects will receive cabozantinib orally at a (starting) dose of 60 mg once daily, on a continuous basis.

Proprietary Information of MD Anderson

Cabozantinib must be taken on an empty stomach. Subjects must be instructed not to eat for at least 2 hours before and at least 1 hour after taking cabozantinib. Subjects should be instructed to take their cabozantinib dose at approximately the same time every day. If a subject misses a dose, the dose may be taken later only if it is within 12 hours of when the missed dose should have been taken. The missed dose should not be made up if it is within 12 hours of the next scheduled dose.

Cabozantinib tablets should be swallowed whole with at least 8 ounces of water. The tablets should not be crushed. Grapefruit, grapefruit juice, Seville oranges and their products should be avoided by subjects taking cabozantinib.

In all subjects, dose reductions and delays to manage toxicity are allowed under the guidelines in Section 3.3 below.

3.3 Cabozantinib Dose Modifications, Interruptions, and Discontinuation

Subjects will be monitored for AEs from the time of from the time of first study intervention through their last follow-up visit (30 days after the date of the last dose of cabozantinib treatment.) Subjects will be instructed to notify their physician immediately at the onset of any AE. Causality assessment of AEs will be determined by the investigator. AE severity will be graded by the investigator in accordance with CTCAE v.4.0.

The following should be taken into consideration in decisions regarding dose modifications (reductions or interruption):

- As a general approach all AEs should be managed with supportive care at the earliest signs of toxicity considered related to the study treatment. Should this be ineffective, dose interruptions and/or reductions should be considered to prevent worsening of toxicity.
- Dose modification criteria for cabozantinib are shown in Table 3-3. Dose interruptions and/or reductions should be implemented for unacceptable toxicity. Doses may be modified at any time while a subject is on treatment.
- The assigned starting dose for cabozantinib is 60 mg/day. 2 dose reduction levels of cabozantinib are permitted (see Table 3-2).
- Dose reductions or interruptions may also occur in the setting of lower grade toxicity than defined in Table 3-3, if the investigator feels it is in the interest of a subject's safety and will optimize drug tolerability.
- Interruption of cabozantinib treatment for cabozantinib-related AEs may occur at any time per investigator discretion. If treatment is interrupted due to related AEs for more than 6 weeks, cabozantinib should be discontinued unless there is unequivocal evidence that the subject is benefitting. In this situation, a subject may be able to restart therapy with a dose reduction upon resolution of the toxicity per the discretion of the investigator.
- Dose interruptions for reason(s) other than related AEs (e.g., surgical procedures) can be longer than 6 weeks per the discretion of the investigator.
- Considering the possibility mitotane induction of CYP3A4 that can reduce cabozantinib levels, subjects who used mitotane within 6 months of study participation will have PK levels (obtained on day 1 and day 29+/- 5 days) analyzed after collection to allow increasing

Proprietary Information of MD Anderson

cabozantinib dose to 80 mg a day if AUC for plasma cabozantinib was <50% of expected AUC provided AE levels are \leq grade 1. Further dose titration in these subjects to 60 mg, 40 mg and 20 mg will be done based on tolerability and adverse effects. The remaining study participants will have their samples analyzed after completing study enrollment.

•

Guidelines for the management of specific AEs are provided in Section 3.3.2.

Table 3-2: Dose Reductions of Cabozantinib

Assigned dose	First Dose Level Reduction	Second Dose Level Reduction
60-mg cabozantinib oral qd qd, once daily Cabozantinib should be discontinued if a qd dose of 20-mg cabozantinib (minimum dose) is not tolerated	40-mg cabozantinib oral qd	20-mg cabozantinib oral qd

Proprietary Information of MD Anderson

Table 3-3: Dose Modifications of Cabozantinib for Treatment-Related AEs

CTCAE v.4.0 Grade	Recommended Guidelines for Management ^a
Grade 1 AEs	Add supportive care as indicated. Continue cabozantinib treatment at the current dose level if AE is manageable and tolerable.
Grade 2 AEs which are tolerable and are easily managed	Continue cabozantinib treatment at the current dose level with supportive care.
Grade 2 AEs which are intolerable and cannot be adequately managed	
At the discretion of the investigator, cabozantinib should be dose reduced or interrupted.
 
Note: It is recommended that dose holds be as brief as possible.

Grade 3 AEs (except clinically non-relevant laboratory abnormalities)	
Cabozantinib should be interrupted unless the toxicity can be easily managed with a dose reduction and optimal medical care. Resume cabozantinib following recovery to Grade 1 (or baseline).
 
Note: It is recommended that dose holds be as brief as possible.

Grade 4 AEs (except clinically non-relevant laboratory abnormalities)	
Subjects should have cabozantinib interrupted immediately.
 
Discontinue cabozantinib unless the following criteria are met:
 
 • Subject is deriving clear clinical benefit as determined by the investigator and agreed by the MD Anderson IND Office • Toxicity can be managed with a dose reduction following recovery to Grade 1 (or baseline) and optimal medical care

AE, adverse event.

Note: The dose delay and modification criteria for specific medical conditions are provided in Section 3.3.2. For re-treatment criteria of study treatment after a dose hold see Section 3.3.1.1.

^a Study treatment dose adjustment is only needed if the toxicity was deemed related to cabozantinib treatment or had an unclear relationship to cabozantinib treatment.

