3.3.1.1 Cabozantinib Dose Reinstitution and Reescalation

If the subject recovers from his or her toxicities to CTCAE v.4.0 Grade ≤ 1 or to the baseline value (or lower) and the toxicity was unrelated to study treatment, then study treatment may be restarted with no change in dose.

Proprietary Information of MD Anderson

If the subject recovers from his or her toxicities to Grade ≤ 1 or to the baseline value (or lower) the toxicity was deemed possibly related to study treatment, then study treatment may be restarted at a reduced dose (see Table 3-2 for the schedule of dose reductions).

Subjects receiving a daily dose of 20 mg may be restarted at the same dose if deemed safe at the discretion of the investigator. Subjects unable to tolerate a daily dose of 20 mg should discontinue study treatment.

Re-escalation to the previous dose, (but not higher than 60 mg/day) may be allowed at the discretion of the investigator and agreement of the MD Anderson IND Office for AEs which have resolved or recovered to \leq Grade 1 (or baseline value) and deemed tolerable and easily managed by optimized supportive treatment. Dose re-escalation is not allowed for a drug-related dose reduction triggered by Grade 4 hematologic toxicities or by Grade 4 AEs affecting major organs (e.g., central nervous system, cardiac, hepatic, and renal).

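### After a related Grade 4 adverse event at 20 mg, Table 3-3 leads to discontinuation, but Section 3.3.1.1 lets the investigator restart the same dose

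*Combined protocol and SAP*

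**What the plan says.** In Section 3.3, the Grade 4 row of Table 3-3 calls for immediate interruption and then discontinuation unless two criteria are met. The first is "Subject is deriving clear clinical benefit as determined by the investigator and agreed by the MD Anderson IND Office". The second is "Toxicity can be managed with a dose reduction following recovery to Grade 1 (or baseline) and optimal medical care". The row leaves out laboratory abnormalities without clinical relevance. Footnote a sets the causality condition: "Study treatment dose adjustment is only needed if the toxicity was deemed related to cabozantinib treatment or had an unclear relationship". A note under the table adds: "For re-treatment criteria of study treatment after a dose hold see Section 3.3.1.1".

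Section 3.3.1.1 says that once a possibly related toxicity has recovered to Grade 1 or baseline, "then study treatment may be restarted at a reduced dose". It continues: "Subjects receiving a daily dose of 20 mg may be restarted at the same dose if deemed safe at the discretion of the investigator". The next sentence reads: "Subjects unable to tolerate a daily dose of 20 mg should discontinue study treatment". The note in Table 3-2 says much the same ("Cabozantinib should be discontinued if a qd dose of 20-mg cabozantinib (minimum dose) is not tolerated"), and Section 2.5 lists inability to tolerate 20 mg among the reasons for mandatory discontinuation.

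**The concern.** A patient taking 20 mg has a related Grade 4 event and recovers. One rule ends treatment. The other, reached by following the table's own cross-reference, allows the investigator alone to resume the dose at which the event occurred.

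What is at stake is the safety of rechallenge and who must agree to it. Reporting the event to the IND Office as serious (Section 6.1.2) informs that office but does not obtain its agreement to a restart. Section 5.6 requires dose changes made by a local physician to be approved by the institution's physician investigator, not by the IND Office.

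**Working it through.** The plan states no figure on this point, so the check sets the rules side by side and counts dose levels.

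1. **Reductions left at 20 mg.** Table 3-2 gives 60 to 40 to 20 mg, which is two reductions. Section 3.3 lets some recent mitotane users go to 80 mg, and their ladder is 80 to 60 to 40 to 20 mg. Section 2.5 sets 20 mg as the minimum. On either ladder, 0 reductions remain at 20 mg.

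2. **Table 3-3, Grade 4 row, at 20 mg.** The second criterion needs a dose reduction, and none exists. It fails however clear the benefit and whatever the IND Office thinks. Result: discontinue.

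3. **Section 3.3.1.1, same patient, recovered to Grade 1.** The reduced-dose restart is unavailable. The sentence that follows offers the same dose on one condition, the investigator's judgement that it is safe. It sets no grade limit, benefit test or IND Office agreement. Result: restart at 20 mg allowed.

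4. **Does other text settle it?**
   - The intolerance rule appears in Section 2.5, Table 3-2 and Section 3.3.1.1, and none of these ties intolerance to a grade. A Grade 4 event may be read as intolerance, but no text says so. The same-dose sentence itself shows that a hold at 20 mg does not automatically count as intolerance.
   - The protocol can be specific where it wants to be. Section 3.3.2.3 stops treatment when related liver enzyme or bilirubin elevations of Grade 3 or higher recur at the lowest dose.
   - In Section 3.3.1.1, re-escalation needs IND Office agreement and is barred after reductions triggered by Grade 4 hematologic or major-organ events. The same-dose restart carries neither safeguard.
   - No sentence gives Table 3-3 precedence over Section 3.3.1.1, and the table's own column is labelled as recommended guidelines.

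5. **Which events are open?**
   - Not affected: events with mandatory permanent discontinuation in Section 3.3.2, and serious, life-threatening rhabdomyolysis (Section 3.3.2.18).
   - Separate rule: pulmonary embolism and deep vein thrombosis, which have their own resumption terms in Section 3.3.2.9.
   - Open: toxicities that the protocol sends back to Table 3-3, such as diarrhea, nausea and vomiting, fatigue, anorexia and weight loss (Section 3.3.2.5), and clinically relevant hypophosphatemia (Section 3.3.2.12).
   - Also open, where Grade 4: liver and QTc events. Their own rules (Sections 3.3.2.3 and 3.3.2.11) provide for restart at a reduced dose, which does not exist at 20 mg. The liver stop at the lowest dose applies only on recurrence, so a first Grade 4 liver event is not covered by it.

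**The case against.** The strongest reply is that the texts work in sequence. Table 3-3 decides who is discontinued, and Section 3.3.1.1 applies only to patients still on a hold. A patient whom the Grade 4 row has discontinued never reaches the restart sentence. That sentence is permissive and has an ordinary use without Grade 4. Table 3-3 provides for holds after intolerable Grade 2 and Grade 3 events, and without the sentence a patient held at 20 mg for such an event could not resume. Treating a related Grade 4 event at the minimum dose as tolerated would also be strained.

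Most of this stands. Taking Table 3-3 as the gate is the better reading, and the restart sentence should keep its lower-grade use. What remains is that the protocol does not state the gate. The sentence also sits directly after the reduced-dose rule, so it reads as the answer to the case where no reduction is left, which is exactly where the Table 3-3 criterion fails.

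A reader might infer that the two texts conflict at every dose, because Section 3.3.1.1 does not repeat the benefit and IND Office criteria. The documents do not support that. Above 20 mg a reduction is available, so the table's criteria and the reduced-dose restart fit together in sequence.

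**Conclusion.** The point holds for 20 mg only, as a conflict between two stated safety rules. It is minor in severity and a cheap improvement for patient safety. It rests on the wording as it stands and on there being no rule of precedence.

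The number affected is small and may be zero. A patient must be at 20 mg, have a clinically relevant Grade 4 event that is related or of unclear relationship, recover, and have no separate rule that settles the matter, in a trial of at most 18 (Section 7.3). The documents give neither the share reaching 20 mg nor the rate of related Grade 4 events, so no probability can be calculated. The dose-reduction rate quoted in Section 1.2.3.4 for the renal cell phase 3 study does not help. It counts any reduction, in a different tumor, and patients here can also step down by 20 mg for ketoconazole use without any toxicity (Sections 3.4.3 and 3.4.4).

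A reader might also infer that the primary analysis or the stopping rule is compromised. The documents do not support that. PFS4 is defined by progression or death, and Table 7-1 counts toxicities observed. Whether a patient later resumes 20 mg is an input to neither.

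**What to change.** Amend the 20 mg sentence in Section 3.3.1.1 so that the same-dose restart, at the investigator's judgement, applies after events of Grade 3 or lower. Then add wording to this effect: *After a Grade 4 event that is related or of unclear relationship, other than a laboratory abnormality without clinical relevance, the Grade 4 criteria of Table 3-3 govern and same-dose restart at 20 mg is not allowed. Pulmonary embolism and deep vein thrombosis remain under Section 3.3.2.9.*

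Liver and QTc events should not be exempted, because an exemption would leave the same gap open for them at 20 mg. The mandatory discontinuations in Section 3.3.2 need no change.

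The cost is a short amendment to one paragraph, with no extra data, visits or patients. The downside is that a rare patient benefiting at 20 mg loses a restart, but Table 3-3 already withholds it. If the sponsor wants that restart to be available, the protocol should say so and state whether IND Office agreement is required.
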